#### *Missing Values*

Since data will be prospectively collected, we anticipate that data will be nearly complete, particularly for the safety outcomes. We will explore imputing any laboratory values that are missing up to two visits in the middle of the follow-up period using linear or non-linear interpolation, as appropriate. To interpolate direct and total bilirubin, we will primarily use the two closest observations, since bilirubin could be very different in points in time located further apart from the missing observation. We will compare conclusions of analyses based on imputed values with analyses based on the available information.

[name], Department of Surgery, Children's Hospital & Medical Center  
 [name], Department of Surgery, Children's Hospital & Medical Center  
 [name], Pediatric Research Office, Dept. of Pediatrics, UNMC  
 [name], Department of Biostatistics, College of Public Health, UNMC

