### **D. Definition of Primary and Secondary Outcomes/Endpoints**

Generally, primary safety analyses will be based on time from baseline or 30 days after baseline until two months after patients first reached direct bilirubin levels  $< 2$  mg/dL. Baseline will be defined as information collected at the date that treatment starts for Omegaven® patients and on the date that patient reached bilirubin levels  $> 2$  for soybean oil fat emulsion patients. Information on mortality and transplant will be collected during the whole treatment with Omegaven®. Primary efficacy analysis will include time from baseline until the patient normalizes bilirubin (presents three consecutive direct bilirubin  $\leq 2$  mg/dL or a direct bilirubin  $\leq 2$  mg/dL and weaned from TPN).

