#### *Analysis of Efficacy of Omegaven®*

The primary outcome to gain preliminary evidence of efficacy will be based on the time from baseline to normalization of bilirubin level, i.e., first time point among three consecutive in which bilirubin is < 2 mg/dL. We do not anticipate that any subject will present a rebound on direct bilirubin after normalization. However, we will describe the cohort with respect to the frequency of rebounds in bilirubin levels.

Time to normalize direct bilirubin levels will be estimated using Kaplan-Meier curves. We will estimate hazard ratios and adjust for potential baseline confounders using Cox-proportional hazard models. For all survival analysis based on non-parametric or semi-parametric methods, we will attribute an infinite time to event for subjects who die or receive a liver transplant before bilirubin is normalized. Subjects who die before their bilirubin levels normalize (particularly due to liver failure) have in fact the worst outcome (infinite time to normalize bilirubin) and were not censored before reaching the endpoint of interest. Results of these analyses will be compared with results of analysis excluding subjects who die or are transplanted. Time to reach a total bilirubin of 1.2 will also be estimated using survival analysis methods. Analyses of this outcome will proceed as described for direct bilirubin.

We will also describe individual profiles over time (i.e., 2 months before baseline or birth until end of follow-up period) for all subjects using graphical methods. Trends in liver function markers over time will be explored using generalized linear models in which correlations of observations within subjects will be accounted using a generalized equations or random effects approach. We will perform these analyses including only subjects who did not die or undergo transplantation and including all subjects but assigning for subjects who died or underwent a transplant their worse possible outcome after they died or had the transplant. Using descriptive statistics, we will also explore the association between spikes in blood tests over time and predictors including transfusions of red blood cell products and blood stream infections.

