#### *Statistical Power and Sample Considerations*

The number of subjects included in the study will be based on a compassionate use protocol and not on study power considerations. The primary safety analysis will be descriptive and not based on statistical significance. However, in Table 4 we outline power to detect several differences in the frequency of adverse events, assuming 20, 25, or 30 patients, diverse proportion of subjects with adverse event in either treatment period and not with the adverse event in either treatment period and not with the adverse event in the other (proportion of discordant pairs), for a two-sided 5% significance level McNemar's tests.

For lower proportions of discordant pairs, we would generally attain close to 80% power in McNemar's test. Even for higher proportions of discordant pairs, assuming the high differences between before and after treatment that we expect to observe, e.g., 50% or more, 80% power can be attained in McNemar's test (Table 4).

Table 4—Power to detect varying differences in proportions before and after treatment with Omegaven® in a McNemar's test. All calculations based on an alpha significance level of 0.05

Difference between proportions	Proportion of discordant pairs	McNemar's Test		
		Sample Size		
		20	25	30
30%	40%	59%	72%	81%
	60%	44%	55%	63%
50%	60%	92%	97%	99%
	80%	79%	88%	93%
80%	85%	>99%	>99%	>99%
	95%	>99%	>99%	>99%

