**Table 3: Suggested Monitoring Schedule for Omegaven® Therapy**

Parameter	Baseline (pre- Omegaven)	Daily	Q week* Until direct Bili < 2mg/dL	Monthly* once direct bilirubin <2.0 mg/dL	Periodically*	Tube type volume
Weight	X	X				
Fluid balance	X	X				
Vital Signs	X	X				
Catheter site/function	X	X				
Laboratory test:						
Sodium	X		X	X		
Potassium	X		X	X		
Chloride	X		X	X		
Glucose	X		X	X		
BUN	X		X	X		
Creatinine	X		X	X		
Triglycerides	X		X	X		
Calcium	X		X	X		
Magnesium	X		X	X		
Phosphorus	X		X	X		
Prealbumin	X		X	X		
C reactive protein	X		X	X		
Albumin	X		X	X		
Total protein	X		X	X		
SGPT	X		X	X		
Alkaline phosphatase	X		X	X		
Bili (total and direct)	X		X	X		
GGT	X		X	X		
AST	X		X	X		
Ess. Fatty Acid Profile	X		X	X		2 mL red top
Free cholesterol	X		X	X		
Free fatty acids	X		X	X		
Lipid Panel	X		X	X		
Hemoglobin	X		X	X		0.6ml purple top
Hematocrit	X		X	X		
RBC	X		X	X		
WBC	X		X	X		
Platelets	X		X	X		1.5ml blue top
PT	X		X	X		
PTT	X		X	X		
INR	X		X	X		
Fibrinogen	X		X	X		Navy blue Metal free
Selenium					X	
Zinc					X	
Aluminum					X	
Copper					X	lithium heparin
Iron					X	
Carnitine					X	
Vitamins A,D,E					X	
Retinol binding protein (check when getting Vit A)					X	3 ml red top

\*More often as necessitated by clinical course; may be reduced in patients who are stable (i.e., home patients) and whose biochemical markers have improved.

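### Interpolated bilirubin values are not barred from the three-value normalisation run, so a primary efficacy event can rest on one measured low value and be dated to a visit with no blood draw

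*Protocol*

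**What the plan says.** **Event.** Section D (Definition of Primary and Secondary Outcomes/Endpoints) states: "Primary efficacy analysis will include time from baseline until the patient normalizes bilirubin". It defines this as three consecutive direct bilirubin values at or below 2 mg/dL, or one such value in a child weaned from TPN. The Analysis of Efficacy section dates the event to the "first time point among three consecutive in which bilirubin is < 2 mg/dL". The mismatch between the two thresholds is a separate matter and does not affect this point.

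**Missing data.** The Missing Values section states: "We will explore imputing any laboratory values that are missing up to two visits in the middle of the follow-up period". The method is left open: "using linear or non-linear interpolation, as appropriate". The section then addresses the endpoint variable itself: "To interpolate direct and total bilirubin, we will primarily use the two closest observations". It closes with a safeguard: "We will compare conclusions of analyses based on imputed values with analyses based on the available information".

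**Spacing of draws.** Table 3 suggests bilirubin draws "Q week* Until direct Bili < 2mg/dL" and monthly thereafter. The Reversal Study Lab Schedule likewise has weekly draws for patients on Omegaven with direct bilirubin at or above 2 mg/dL. Below that level, the outpatient schedule is monthly.

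No section says that the three values must be measured, that filled values may not enter the run, or that the event date must be a draw date.

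**The concern.** A three-value rule exists so that one low reading does not count as normalisation: two further readings must confirm it. The permitted gap, two visits, equals the number of confirming values needed. Interpolation can therefore supply all of the confirmation, calculated from the measured values on either side of the gap.

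Two things are at stake. First, the date of a time-to-event outcome can fall on a day when no blood was taken. Second, a child can be declared normalised when the next real measurement shows that the level is back above 2 mg/dL. For the gaps that the rule fills, linear interpolation between two values below 2 always stays below 2. It cannot break a run of measured low values, so it leaves a child's event date unchanged or moves it earlier.

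**Working it through.** The protocol gives no figure on this point, so there is none to reproduce. The check applies the stated fill rule to the stated event definition.

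**1. Fill formula.** Let *a* be the measured value before a gap of two equally spaced visits and *b* the measured value after it. Linear interpolation gives

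- first filled value: (2*a* + *b*)/3
- second filled value: (*a* + 2*b*)/3

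**2. Falling case** (*a* ≥ 2 > *b*). The first filled value is the larger, so both are below 2 when (2*a* + *b*)/3 < 2, that is, *a* < 3 − *b*/2.

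- *b* = 0.5: *a* below 2.75
- *b* = 1.0: *a* below 2.5
- *b* = 1.5: *a* below 2.25

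Example with *a* = 2.4 and *b* = 1.0: (4.8 + 1.0)/3 = 1.93 and (2.4 + 2.0)/3 = 1.47. The series reads 2.4, [1.93], [1.47], 1.0. This is a complete run with one measured value below 2, dated two visits before that value.

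The protocol also allows non-linear interpolation. On the log scale the condition is *a*²*b* < 8, or *a* < √(8/*b*), which gives 4.0, 2.83 and 2.31 for the same three values of *b*. The open choice of method therefore changes which children qualify.

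A steep fall does not trigger the problem under linear filling: *a* = 5.0 and *b* = 0.5 give [3.5] and [2.0], neither below 2.

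**3. Rebound case** (*a* < 2 ≤ *b*). By symmetry both filled values are below 2 when *b* < 3 − *a*/2. With *a* = 1.0 and *b* = 2.4: (2.0 + 2.4)/3 = 1.47 and (1.0 + 4.8)/3 = 1.93. The series 1.0, [1.47], [1.93], 2.4 completes a run. The event is dated to a real draw, but the only measured value that follows contradicts it.

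**4. How far an event can be pre-dated.** An event falls on an undrawn visit only if the last measured value before the gap is at or above 2; otherwise that measured value would itself open or belong to the run. Patients at that level are scheduled for weekly draws. Two filled weekly visits put the event at most 2 × 1 = 2 weeks before the next measured low value. The distance to the date under a measured-only rule can be longer if that low value is followed by a rebound.

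**5. How often.** This needs inputs that the protocol does not give. Assumptions: direct bilirubin starts near 4 mg/dL, the log slope is −0.15 to −0.4 per month, noise SD is 0.2 (mg/dL or log scale), values are missing at random, and draws are weekly at or above 2 and monthly below. Compared with a measured-only run:

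| Values missing | Events dated earlier |
|---|---|
| 5% | about 3–4% |
| 10% | about 6–7% |
| 20% | about 10–15% |

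The median shift among the affected events was one week. No event was created in a child who had none on measured values.

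**6. In children.** The number of patients is not set by power ("The number of subjects included in the study will be based on a compassionate use protocol and not on study power considerations"), but Table 4 considers 20 to 30. If all reach normalisation, 5% missing affects about one child (20 × 0.03 = 0.6 to 30 × 0.04 = 1.2), and 20% missing affects two to four or five (20 × 0.10 = 2 to 30 × 0.15 = 4.5).

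**The case against.** The case for leaving the text alone has several parts.

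- **The wording is tentative and hedged.** The team will only explore imputation, and it commits to a comparison with available-data results, which should expose any effect. This limits the harm. It does not say which result stands if the two differ, and the choice between linear and non-linear filling is also open.
- **Data are expected to be nearly complete.** If so, the effect is very small. But this is an expectation, expressed most strongly for the safety outcomes, and the same argument makes a measured-only rule almost free.
- **Single-value events already exist.** One low value in a child weaned from TPN counts under Section D. That is true, but the weaning route does not date an event to a day without a draw.
- **An earlier date may be nearer the truth.** If bilirubin is 2.4 before a gap and 1.0 after it, the crossing did occur inside the gap, and dating at the next draw is late. This stands as an argument for interval censoring as a sensitivity analysis. It does not justify letting calculated values serve as confirmation.
- **Such detail may belong in an analysis plan that is not shown.** Silence alone would not be a finding. Here, however, the protocol itself fixes the fill rule, names the endpoint variable and defines the run, and the two rules conflict in purpose.

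A reader might also infer three stronger points that the protocol does not support. The first is that events could be pre-dated by two months on monthly draws. That would need monthly draws while bilirubin is still at or above 2, whereas the schedule has weekly draws there; only the discretionary footnote to Table 3 for stable, improved patients could allow otherwise. The second is that using the two closest observations permits extrapolation from two earlier draws, even to a negative value. The section speaks of interpolating in the middle of follow-up, which means between flanking observations. The third is that the bias favours Omegaven over conventional emulsion. The primary hypothesis is comparative, and shorter times help one group only if missingness or filling differs between the groups, which nothing in the protocol shows.

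**Conclusion.** The point holds, at modest size. As written, two interpolated values and one measured low value can make a primary efficacy event, date it to an undrawn visit, or declare normalisation just before a measured value above 2 mg/dL. The arithmetic for this is exact and needs no assumption beyond linear filling of equally spaced visits.

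The frequency depends on the assumed trajectories, noise and random missingness: a few per cent of events at 5% missing, and 10–15% only if a fifth of values are missing, a level that the protocol does not suggest. The typical shift of one week relies on the weekly schedule being followed. The defect concerns how the endpoint is defined and confirmed. The figures do not suggest that it would overturn the efficacy result.

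**What to change.** Add one sentence to Analysis of Efficacy: in the primary analysis, the three consecutive values are measured values and the event is dated to the first of them. Add one sentence to Missing Values: interpolated bilirubin, always calculated between one observation before and one after the gap, is used only for plots, trend descriptions or a labelled sensitivity analysis. Missed draws around the crossing can be examined in an interval-censored sensitivity analysis.

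Under this rule the series 2.4, missing, missing, 1.0 is not yet an event. Its earliest possible date is the measured 1.0, provided that the next two measured values are also below 2. The series 1.0, missing, missing, 2.4 is no longer an event.

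The cost is two sentences and a few events dated slightly later. No change to the visit schedule or to patient care is needed.

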### Outcome/Endpoints

#### *Treatment safety*

Our primary outcome for treatment safety will be based on patient's essential fatty acid profile. We will compare patients before treatment with Omegaven® started and after treatment started (one month after treatment started until treatment stopped) with respect to the frequency with which triene/tetraene ratio  $> 0.2$  at any time. Primary analyses for these and all other safety outcomes will be based on a follow-up time for Omegaven® starting 30 days after baseline, i.e., 30 days after treatment started for Omegaven® patients and 2 months after the first direct bilirubin level  $< 2$  mg/dL was recorded.

Additional comparisons across treatment periods for subjects receiving Omegaven® will be aimed to assess occurrence of spontaneous bleeding (e.g., unexplained bruising, oozing from gums/incision sites), and maximum triene/tetraene ratio, minimum platelets, maximum international normalized ratio (INR), and trends in pre-albumin (age standardized levels). We will also explore trends in coagulopathies based on curves of platelets, prothrombin time (PT), partial thromboplastin time (PTT) over time, and INR. We will also describe the rate with which INR ratios were  $> 2$  (number of days/follow-up time), as a marker of coagulopathies.

Additional evaluation of Omegaven® will be performed with regards to rate in which albumin is  $> 3$  g/dL, maximum triglyceride level, rate of blood stream infections (number of positive blood cultures/follow-up-time under PN after baseline), rate of central venous catheter (CVC) infections (number of CVC infections/follow-up time and number of gram positive CVC infections/follow-up time), and occurrence of anaphylactic reactions after baseline.

We will describe trends over time for all outcomes associated with fatty acid profiles (including triene/tetraene ratios, triglycerides, total omega-6 fatty acids, total omega-3 fatty acids, total saturated, total monounsaturated, and total polysaturated fatty acids). Specific fatty acids such as arachidonic, palmoleic, palmitic, oleic, stearic, and linoleic fatty acids will also be evaluated and described.

[name], Department of Surgery, Children's Hospital & Medical Center  
[name], Department of Surgery, Children's Hospital & Medical Center  
[name], Pediatric Research Office, Dept. of Pediatrics, UNMC  
[name], Department of Biostatistics, College of Public Health, UNMC

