### *Analysis of Safety and Tolerability of Omegaven®*

All primary safety and tolerability analyses will be based on descriptive statistics. In secondary analyses, we will also assess the statistical significance of differences. The period receiving Omegaven® will start 30 days after beginning PN with Omegaven® for the main analysis. Outcomes measured in the Omegaven® will be described for a period starting 30 days after baseline.

Primary outcomes measured will include whether the triene/tetraene ratio was ever  $> 0.2$  during the intervention period and whether the INR was ever  $> 2$ . Secondary outcomes measured will include platelets, prothrombin time (PT), partial thromboplastin time (PTT), and other components of the fatty acid profile. Analysis of all categorical outcomes will be based on proportions and of all continuous outcomes will be based on means or medians of the individual mean, maximum or minimum values, as appropriate, during the respective follow-up period. Comparisons between periods (pre and post-treatment) will be performed based on paired tests, parametric or non-parametric, as appropriate. We will also explore trends over time (e.g., decreasing for INR and increasing for pre-albumin) and estimate p-values via regression models using generalized estimating equations or random effects to account for within subject correlations. When describing outcomes over time, we will explore the effect of predictors of poor hepatic outcomes, such as use of antifungal agents (e.g., amphotericin) and antidiarrheal agents (e.g., loperamide), on potential spikes.

[name], Department of Surgery, Children's Hospital & Medical Center  
[name], Department of Surgery, Children's Hospital & Medical Center  
[name], Pediatric Research Office, Dept. of Pediatrics, UNMC  
[name], Department of Biostatistics, College of Public Health, UNMC

We will also evaluate nutritional outcomes including difference in weight-for- age Z-scores and height-for-age Z-scores from baseline to the moment in which the child starts enteral feeding and to the moment in which the child receives less than 10% of their calories from PN. Using linear regression, we will explore adjustment for baseline alternative predictors of interest. Trends over time in Z-scores will also be explored using regression with repeated measure methods.

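### For the 'ever above threshold', maximum and minimum safety outcomes, comparing interpolated with available laboratory data does not test robustness

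*Protocol*

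**What the plan says.** The protocol's Missing Values section (Data Analysis Plan) opens with an expectation: "we anticipate that data will be nearly complete, particularly for the safety outcomes." It gives no rate. It continues "We will explore imputing any laboratory values" for values "that are missing up to two visits in the middle of the follow-up period using linear or non-linear interpolation, as appropriate." A rule about which neighbours to use is given for one analyte only: "To interpolate direct and total bilirubin, we will primarily use the two closest observations." The section closes with its only missing-data check: "We will compare conclusions of analyses based on imputed values with analyses based on the available information."

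The outcomes to which this applies are set elsewhere in the protocol:

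- Analysis of Safety and Tolerability of Omegaven names as primary whether the triene/tetraene ratio ever exceeded 0.2 and whether the INR ever exceeded 2. It summarises continuous outcomes by "means or medians of the individual mean, maximum or minimum values, as appropriate."
- Outcome/Endpoints, Treatment safety, adds the maximum triene/tetraene ratio, minimum platelets, "maximum international normalized ratio (INR") and the maximum triglyceride level. It also lists a rate of days with INR above 2, and trends over time.
- The main safety window starts 30 days after baseline.

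**The concern.** An 'ever', maximum or minimum outcome is decided by a child's most extreme value. Interpolation estimates a missing value from its neighbours and so tends to smooth between them. The chosen method therefore does not suit the outcomes that matter most for safety. If the filled values cannot alter the outcome, agreement between the two analyses is fixed in advance and says nothing about whether missing draws matter. A true crossing at a missed draw is absent from both analyses.

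The effect on the on-treatment 'ever' proportion runs one way: missed on-treatment draws can only lower it. Hypothesis 1.1 expects the rate of fatty acid deficiency on Omegaven to be as low as before. With the 20 to 30 patients considered under Statistical Power and Sample Considerations, one reclassified child moves a proportion by 1/30 = 3.3 to 1/20 = 5 percentage points. Missed draws are plausible for home patients, whose blood is drawn through home-care agencies and whose results are faxed in.

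**Working it through.** The protocol gives no missingness rate and no figure for this check, so there is nothing to reproduce. Table 4 (McNemar power) does not bear on it. The thresholds, interpolation rule and window come from the protocol. Everything marked as assumed does not.

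**1. Linear fill, both neighbours inside the window.** The filled value is y* = w·y_a + (1 − w)·y_b with 0 ≤ w ≤ 1, so min(y_a, y_b) ≤ y* ≤ max(y_a, y_b). It cannot exceed the observed maximum, fall below the observed minimum, or cross a threshold that no observed value crossed.

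Example: ratios 0.08, 0.18, missing, 0.18, 0.08.
- Linear fill: 0.18. The maximum stays 0.18 and 'ever > 0.2' stays negative.
- The mean does move, from 0.52/4 = 0.13 to 0.70/5 = 0.14.

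**2. Non-linear fill.** Take equally spaced visits t = 0, 1, 2, 3, 4 with t = 2 missing. The cubic spline through these four symmetric points reduces to y = a − b(t − 2)².
- Ratios as above: a − b = 0.18 and a − 4b = 0.08, so b = 0.0333 and a = 0.213, above 0.2.
- INR 1.2, 1.9, missing, 1.9, 1.2: a − b = 1.9 and a − 4b = 1.2, so b = 0.233 and a = 2.13, above 2.

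Both are primary safety events that no sample showed. A shape-preserving cubic gives 0.18 for the ratio example, so the result depends on which curve is called appropriate.

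**3. Neighbour outside the window.** Baseline ratio 0.50, day 30 missing, day 60 = 0.10. Linear fill at day 30 gives (0.50 + 0.10)/2 = 0.30, a new crossing inside the window. The protocol does not say whether a value before day 30 may serve as a neighbour.

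**4. Simulation with correlated values.** Assumed: 20,000 children, 8 monthly ratios, log-normal with median 0.08, between- and within-child log-SD 0.5 each, interior visits missing at random, and gaps of up to two visits filled.

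| | 5% missing | 15% missing |
|---|---|---|
| Children with a filled value | 5,338 | 12,256 |
| Linear or shape-preserving cubic: maximum, minimum or 'ever' changed | 0.0% | 0.0% |
| Ordinary cubic spline: maximum changed | 14.8% | 19.0% |
| Ordinary cubic spline: minimum changed | 22.9% | 26.5% |
| Ordinary cubic spline: 'ever > 0.2' newly positive | 2.3% | 2.7% |
| True 'ever > 0.2', all children | 35.7% | 35.6% |
| Observed 'ever > 0.2', all children | 35.0% | 33.7% |
| Loss, percentage points | 0.7 | 2.0 |

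Linear filling recovers none of the loss, which is about 2% (0.7/35.7) to 6% (2.0/35.6) of true positives.

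**5. Extreme case.** Assumed: six independent log-normal ratios (median 0.08, log-SD 0.6), and every child misses two adjacent interior draws. In 20,000 simulated children, linear filling changed the 'ever' status of none. The true 'ever' proportion was 32.5%, and 29.1% of those children were scored as never exceeding 0.2. With a chance p per draw, 'ever' is 1 − (1 − p)^k:
- p = 5%: 1 − 0.95⁶ = 26.5% falls to 1 − 0.95⁴ = 18.5%.
- p = 10%: 1 − 0.9⁶ = 46.9% falls to 1 − 0.9⁴ = 34.4%.

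**6. Where the comparison can still show something.** Individual means changed in essentially every child with a filled value, under every method. An INR series 2.4, missing, 2.2 fills as 2.3, which adds a value above 2 and so can alter the rate of days with INR above 2. Trends and time to bilirubin normalisation can also move.

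**The case against.** Several points stand against a stronger reading.

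- **Interpolation can never alter these outcomes.** A reader might infer this, but the protocol also allows non-linear interpolation, which can overshoot, and it does not rule out a neighbour before day 30. The two-closest-observations rule covers bilirubin only. Either route can change the result. A change from overshoot reflects the curve and recovers no information about the missed draw.
- **The check is empty as a whole.** It is not. It covers all laboratory analyses and is informative for those in step 6. The protocol does not itself claim that agreement would prove missing draws harmless.
- **The expected loss is 29%.** That figure needs every child to miss a third of the draws, with independent values. The protocol expects nearly complete safety data, and the more realistic scenarios give 0.7 to 2 points.
- **A gap lasts about three months.** That holds for two missed monthly fatty acid profiles under the minimum Safety Labs Schedule. The Reversal Study Lab Schedule lists weekly panels on treatment while direct bilirubin is at least 2 mg/dL, where two missed draws span about three weeks.
- **Interpolation causes the missed peaks.** Any outcome read from intermittent samples can miss a peak, and the protocol nowhere instructs that a missed draw be scored as harmless. The fault is narrower: the stated check cannot reveal that loss.

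It can also be said that the imputation is exploratory, that the primary safety analysis is descriptive, and that the detail could wait for an analysis plan. The first two limit the weight of the point. They do not remove it, because in a descriptive analysis the reported proportion is the result. The third does not answer it, because the protocol itself fixes this method and this comparison.

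**Conclusion.** The point holds for the 'ever', maximum and minimum safety outcomes: triene/tetraene above 0.2, INR above 2, maximum ratio, INR and triglycerides, and minimum platelets. For these, a linear fill between in-window neighbours leaves the result unchanged by algebra, with no distributional assumption. A non-linear fill changes it only through the chosen curve and can invent an event. The planned comparison is therefore not a test of robustness for these outcomes.

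The size rests on assumed inputs. It is about 0.7 to 2 percentage points at 5% to 15% of draws missing at random, and 29% of true positives in the extreme case. It would exceed the random-missingness figures if draws tend to be missed when values are abnormal. The documents do not support saying that the overall safety comparison is biased by a known amount, since missed draws before treatment would lower the pre-treatment proportion as well. This is a worthwhile correction of moderate weight.

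**What to change.** In the Missing Values section:

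1. State that interpolated values will not be used for the 'ever', maximum and minimum safety outcomes. Interpolation may stay for bilirubin, means, trends and descriptive curves.
2. For those outcomes, report scheduled and obtained draws per child in each period, and the proportion of obtained draws above threshold. Name which of the protocol's laboratory schedules defines a missed draw, since the weekly and monthly listings for the fatty acid panel give different counts.
3. As the sensitivity analysis for the 'ever' proportions, give two bounds. In the best case, missed draws are taken as below threshold. In the worst case, a child with a missed scheduled draw and no observed event is counted as an event. Assigning a worst outcome has a precedent in the protocol's efficacy analysis, for children who die or receive a transplant.

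The cost is a change of wording and some extra table rows. The drawback is that the worst-case bound may be wide with 20 to 30 patients. In the simulation above, 5,338/20,000 = 26.7% of children had a filled draw at 5% missing, and 12,256/20,000 = 61.3% at 15%. Among 25 children that is about 7 and 15, less those with an observed event. No dose, schedule or clinical rule changes.
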